7.5.2 Analgesia

Fentanyl is the analgesic agent recommended, but not required, for use in this study. A loading dose of 2 mcg/kg will be administered for both groups at the time the interventions are initiated. Continuous infusion of fentanyl will begin at 2 mcg/kg/hr and maintained at this rate during the initial 4 hour period corresponding to time to cool in the hypothermia group. If required, up to two additional doses of fentanyl 1 mcg/kg may be given. The infusion rate can then be increased by 1 mcg/kg/hr as needed to achieve a Ramsay sedation score of 5.

If the Ramsay score is 6 (no response) after the first four hours of the intervention, the fentanyl drip will be weaned by 1 mcg/kg/hr to achieve a Ramsay score of 5. The lowest infusion dose in the initial 24 hours will be 1 mcg/kg/hr. After 24 hours, the fentanyl infusion may be weaned to off if there is no clinical shivering, patient temperature is in the appropriate target range, and the goal for sedation/analgesia is obtained (Ramsay score of 5).

Other narcotics (e.g., morphine, remifentanyl) may be used as an alternative to fentanyl at the clinical site's discretion. However, the level of analgesia should be based on the Ramsay targets outlined here.

7.6 Use of Neuromuscular Blockade

Vecuronium is the recommended, but not required, neuromuscular blocker for the THAPCA Trials. A paralytic loading dose of 0.1-0.2 mg/kg (100-200 mcg/kg) will be administered to patients randomized to hypothermia to facilitate cooling. Repeated doses of vecuronium will be administered as needed to maintain paralysis until the patient is cooled to the therapeutic range (32-34 °C).

Once therapeutic hypothermia is achieved, neuromuscular blockade is not required, except for as needed to control shivering resistant to sedative/analgesic agents and rewarming without clinical shivering. If a cooled patient begins to rewarm above 34.5 °C in spite of the absence of clinical shivering, vecuronium in a dose of 0.1-0.2 mg/kg (100-200 mcg/kg) would be administered immediately, and continued until the patient cools to the therapeutic range (32-34 °C). Neuromuscular blockade may also be used for other aspects of care at the discretion of the primary care team (such as ventilator asynchrony).

Other non-depolarizing agents may be used during cooling and to control shivering based on the above parameters at the clinical site's discretion.

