7.1 Hypothermia

Patients randomized to receive therapeutic hypothermia (hypothermia group) will have a target temperature of 33 °C plus or minus 1 °C (32 to 34 °C). Hypothermia will be induced using the Blanketrol III cooling unit and Maxi-Therm Lite blankets placed below and over each patient. No internal cooling procedures or devices will be used (e.g., gastric lavage, intravascular cooling catheter). Based on newborn and adult reports that used the Blanketrol II cooling unit, we expect to achieve the target temperature range within 1 to 4 hours of initiating cooling procedures.^{30, 106} For the NICHD Neonatal study, cooling was achieved within 90 minutes³⁰ and in an adult TBI study, 2.8 hours (1.1 to 4.5 hr range) was reported.¹⁰⁶

For patient safety, dual central temperature measurements will be performed. A temperature sensing esophageal probe and temperature sensing Foley catheter (or rectal temperature probe) will be placed for temperature monitoring prior to initiation of cooling. Please note: the esophageal probe is the preferred primary probe which will be connected to the Blanketrol unit. However, in the event that an esophageal probe is not judged to be feasible, the Foley catheter or rectal probe may be used as the primary probe and the remaining probe will be the secondary probe which will be connected to the bedside monitor. For patient safety, the *lowest* value will be assumed correct if there is a discrepancy in measurements. If there is a discrepancy of greater than 2 °C between the two measurements, the temperature probes should be inspected for proper positioning and function. The patient's temperature will be monitored continuously and recorded every 30 minutes until central temperature is 33 °C. If the patient is 33 degree at the time of therapy initiation, the temperature will be monitored every 30 minutes for at least one hour. Thereafter, the temperature will be recorded every hour until rewarming begins.

The hypothermia group will be sedated with midazolam and fentanyl. Other benzodiazepines and narcotics may alternatively be used at the clinical site's discretion. The hypothermia group will be paralyzed with vecuronium until the therapeutic hypothermia temperature range is achieved. Vecuronium for paralysis will be held after the initial cooling period and utilized only as needed for shivering unresponsive to the sedation/analgesia protocol described in Section 7.5 on page 49.

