7.5.1 Sedation

Midazolam is the sedative agent recommended, but not required, for use in this study. A loading dose of 0.1 mg/kg (100 mcg/kg) of midazolam will

be administered for both groups at the time the interventions are initiated. This will be repeated as needed to achieve a Ramsay score of at least 5 (sluggish response to light tap). A continuous IV infusion of midazolam at 100 mcg/kg/hr will be initiated and maintained at this rate or greater during the initial 4 hour period corresponding to time to cool in the hypothermia group. If required, up to two additional doses of midazolam 0.1 mg/kg (100 mcg/kg) may be given. The infusion rate can then be increased by 50 mcg/kg/hr as needed to achieve a Ramsay sedation score of 5.

If the Ramsay score is 6 (no response) after the first four hours of the intervention, the midazolam drip will be weaned by 50 mcg/kg/hr to achieve a Ramsay score of 5. Lowest infusion dose in the initial 24 hours will be 50 mcg/kg/hr. After 24 hours, the midazolam infusion may be weaned to off if there is no clinical shivering, patient temperature is in the appropriate target range, and the goal for sedation/analgesia is obtained (Ramsay score of 5).

Other benzodiazepines (e.g., lorazepam) may be used as an alternative to midazolam at the clinical site's discretion. However, the level of sedation should be based on the Ramsay targets outlined here.

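### Vecuronium indications in Section 7.1 do not match Section 7.6, and the mandatory Ramsay 6 wean in 7.5.1 and 7.5.2 has no exception for a paralysed child

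*Protocol*

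**What the plan says.** Indications. Section 7.1 has the hypothermia group paralysed until the target range is reached. After that, vecuronium is held and "utilized only as needed for shivering unresponsive to the sedation/analgesia protocol". Section 7.6 says that blockade is then not required, "except for as needed to control shivering resistant to sedative/analgesic agents and rewarming without clinical shivering". For the second of these situations it gives a trigger, "If a cooled patient begins to rewarm above 34.5 °C in spite of the absence of clinical shivering", and an action: a dose of 0.1-0.2 mg/kg that "would be administered immediately, and continued until the patient cools to the therapeutic range". The same section leaves blockade for other purposes, such as ventilator asynchrony, to the primary care team.

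Sedation and analgesia. In Section 7.5.1 midazolam starts at 100 mcg/kg/hr and is "maintained at this rate or greater during the initial 4 hour period corresponding to time to cool in the hypothermia group". The section continues: "If the Ramsay score is 6 (no response) after the first four hours of the intervention, the midazolam drip will be weaned". Each step is 50 mcg/kg/hr and aims to bring the score back to 5. The section then sets a floor: "Lowest infusion dose in the initial 24 hours will be 50 mcg/kg/hr". After 24 hours the infusion may be stopped if there is no shivering, temperature is in range and the Ramsay goal of 5 is met. Section 7.5.2 has the same structure for fentanyl: start 2, step 1, floor 1 mcg/kg/hr, and the same conditions for stopping after 24 hours.

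Related orders. Section 7.2 orders a single vecuronium dose in the normothermia arm when temperature exceeds 38.0 °C despite acetaminophen and surface cooling. Section 7.12 gives ECMO patients their own rule, under which paralysis is needed only for shivering that sedation and analgesia have not controlled.

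**The concern.** There are two separate faults. The first is a plain conflict over when the drug is given: staff working from 7.1 would withhold a dose that 7.6 tells them to give at once.

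The second is a titration rule that fails under blockade. The protocol defines Ramsay 6 as no response, and a paralysed child gives none at any depth of sedation. The score then cannot separate paralysis from over-sedation, yet the instruction attached to it is to reduce both drugs. Ramsay is also the only gauge that 7.5.1 and 7.5.2 offer, since sites using other agents are told to work to the same targets.

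What is at stake is a child kept paralysed on reduced sedation and analgesia, or with both infusions already stopped, while the stated measure cannot show it.

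**Working it through.** The protocol gives no figure to reproduce. The check sets the sections side by side, with simple arithmetic on the stated rates and times.

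**1. Indications after initial cooling**

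| Situation | 7.1 | 7.6 |
|---|---|---|
| Shivering not controlled by sedation | allowed | allowed |
| Rewarming above 34.5 °C, no shivering | excluded by the word *only* | ordered immediately |
| Other care, e.g. ventilator asynchrony | excluded by the word *only* | at team discretion |

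Two of the three rows conflict.

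**2. Sedation condition.** The shivering indication (7.1, 7.6) and the ECMO rule (7.12) each presuppose that sedation or analgesia has been tried. The 34.5 °C order has no such step, and neither does the 38.0 °C order in 7.2.

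**3. Ramsay 6 wean, hours 4 to 24.** One step from the starting rate gives:

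- midazolam: 100 − 50 = 50 mcg/kg/hr, equal to the floor;
- fentanyl: 2 − 1 = 1 mcg/kg/hr, equal to the floor.

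Each is half the starting rate (50/100 = 1/2 = 0.5). The floors prevent any further reduction before 24 hours.

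**4. Initial cooling beyond four hours.** Section 7.1 expects target temperature within 1 to 4 hours, so the four-hour hold covers planned paralysis. It also cites a longer adult upper limit: "in an adult TBI study, 2.8 hours (1.1 to 4.5 hr range) was reported". The overrun is 4.5 − 4 = 0.5 h, with both infusions at or above their floors. This part is trivial.

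**5. After 24 hours.** No floor is stated. Arithmetically, one more step from the floor gives 50 − 50 = 0 and 1 − 1 = 0. But the only sentences that permit stopping require temperature in range and Ramsay 5. A child under rescue blockade above 34.5 °C and scored 6 meets neither condition, so a wean to zero at that moment is not clearly what the text says. The clear gap is different: the infusions may have been stopped earlier, when the conditions were met, and temperature may then pass 34.5 °C. Section 7.6 orders paralysis, and no line says to restart sedation or analgesia.

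**6. When such an episode could begin.** I assume the protocol's clock runs from the start of the intervention and that the rescue order applies during maintenance. Maintenance ends at 1 + 48 = 49 h or 4 + 48 = 52 h, or at 72 − 16 = 56 h by counting back from the planned end of rewarming. Counted from hour 24, the windows are 25, 28 and 32 h. This is the period in which an episode could start. It is neither time paralysed nor a measure of frequency.

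**The case against.** The best case against the point is that the protocol plans for sedation throughout. Section 7.1 says the hypothermia group will be sedated with midazolam and fentanyl. Section 7.5 prescribes infusions with intermittent doses through cooling, maintenance and rewarming. Stopping after 24 hours is optional and needs three conditions together, one of them a Ramsay score of 5, so a child whose infusions were properly stopped was already deeply unresponsive. Enrolled children are comatose. Section 7.6 is the dedicated section and 7.1 a summary, so staff would probably follow 7.6, and PICU staff would probably sedate before paralysing. Section 12.2 also promises a manual of operations, which is not at hand and may cover this.

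Much of this stands, and it keeps the point small. It does not remove it. The general sentence in 7.5 is qualified by the specific permission in 7.5.1 and 7.5.2 to stop the infusions. The Ramsay 6 reduction is worded as mandatory and has no temperature or paralysis condition. A manual may add detail, but it should not have to reverse a protocol instruction.

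Two stronger readings are tempting. A reader might infer that the protocol directs a wean to zero in a child under rescue blockade. The conditions for stopping weigh against that, and the text does not settle it. A reader might also infer that it permits paralysis without sedation as a matter of course. The planned background infusions, the 24-hour floors and the continuing availability of intermittent doses do not support that.

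**Conclusion.** The point holds as a minor patient-safety correction. Three things are established from the text: 7.1 and 7.6 disagree on when vecuronium may be given after initial cooling; the Ramsay 6 wean has no exception for a paralysed child; and nothing says to restart infusions that were stopped after 24 hours when rescue blockade is ordered.

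Before 24 hours the consequence is limited to a reduction to the floors. The infusions-off case needs a sequence: both infusions stopped after 24 hours under the stated conditions, a later rise above 34.5 °C without shivering, and staff who do not re-sedate. The protocol gives no basis for estimating how often that would occur. The conclusion assumes literal application of the text, and that a paralysed child scores 6 because the protocol labels that score as no response. ECMO patients fall outside the 34.5 °C finding because of their own rule in 7.12. The point has no bearing on endpoint, sample size, power or alpha.

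**What to change.** 1. In 7.1, replace the single permitted indication with all those in 7.6: sedation-resistant shivering, rewarming above 34.5 °C without shivering, and discretionary use by the primary care team.
2. In 7.6, state that sedation and analgesia must be running or re-established with any neuromuscular blockade and continued while the child is paralysed. Apply the same sentence to the 38.0 °C vecuronium order in 7.2. The agents named for ECMO patients in 7.12 need not change.
3. In 7.5.1 and 7.5.2, state that the Ramsay 6 wean and weaning to off are suspended during blockade, and that sedation is then judged by the clinical team's usual means.

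The clinical leads should settle the wording; no drug or dose is proposed here. The cost is a few sentences in the protocol and matching text in the manual of operations.

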7.7 Management of Glucose and Insulin

An explicit protocol for management of glucose and nutrition is not part of the current protocol at this time. We are aware that large clinical trials of explicit glucose control protocols are ongoing or planned in both adults and pediatric populations at this time. Should information from properly conducted clinical trials become available, which demonstrates efficacy and safety of an explicit protocol approach to glucose management in children, we will consider amending this protocol at that time.

The optimal glucose concentration range following pediatric cardiac arrest and in the more general pediatric critical care population is not known at the time of writing this protocol. It is not known, for example, whether a tight glucose range protocol utilizing insulin would be detrimental in a post arrest pediatric population. In adult populations, there is evidence suggesting hyperglycemia may be associated with poorer neurological outcome after various neurological insults.¹⁰⁸⁻¹¹³ Causality has not been established, however. Furthermore, RCTs in heterogeneous adult ICU settings have so far reported conflicting findings related to tight protocol directed glucose control. Van den Berghe initially reported in a Belgium adult surgical ICU population, tight glucose control to be associated with reduced mortality.¹¹⁴

A more recent report by the same investigator reported glucose control not to be associated with reduced mortality in a medical ICU population.¹¹⁵ A multicenter German RCT (VISEP) of intensive insulin therapy in severe adult sepsis population did not demonstrate efficacy.¹¹⁶ Of note, this trial was stopped early because of no benefit and high rate of hypoglycemia in the treated group (12% versus 2%). No clinical trials have been conducted to assess explicit protocol directed glucose management and survival in a pediatric ICU population. In pediatric animal models, maintaining glucose levels in a low level range was not reported to improve neurological outcome.¹¹⁷

It should be noted that prior adult and neonatal hypothermia RCTs did not report glucose management protocols with the exception of Bernard²⁸ who stated a glucose less than 180 mg/dl was a goal. There are no animal or human data on the effects of tight glucose control combined with hypothermia on clinical outcomes. Hypothermia is known to be associated with both hyperglycemia and improved neurological outcome.

A potential safety issue exists with hypothermia and insulin use. Serum potassium measurements are known to decrease with therapeutic hypothermia cooling and then increase during the subsequent rewarming period. Insulin is known to significantly decrease serum potassium. If insulin is administered for hyperglycemia associated with hypothermia, it is likely to be associated with worsening of hypokalemia and require additional supplements of large amounts of potassium. On rewarming, this may result in a more exaggerated rise in serum potassium measurement. Therefore, the approach to be recommended for sites in the THAPCA Trials will be to pay special attention to serum potassium and glucose concentrations, and manage glucose, potassium, and insulin administration according to usual clinical practice for each PICU, avoiding extremes of glucose and potassium.

7.8 Hemodynamic Management

Blood pressure will be monitored by an arterial line. This is the usual standard practice in PICUs for a post arrest pediatric patient who would meet the study entry criteria. Secure central venous access will be required for participation in this study. This is common practice for the majority of post arrest patients in order to be able to safely and reliably administer fluids, inotropic/vasopressor agents, etc.

It would be desirable to describe an explicit hemodynamic management algorithm for subjects enrolled in THAPCA, but this is untenable due to the diversity of the post arrest pediatric patient population, the multiple etiologies of cardiac arrest, and other comorbid conditions that would be

represented in a typical pediatric population. Of note, explicit hemodynamic protocols were not described in the adult and neonatal RCTs, which demonstrated efficacy of hypothermia for cardiac arrest or HIE.

In general, goal blood pressure for each case will be maintained in a range normal for age and optimized for other factors such as coexisting conditions as determined by the clinical care team. The clinical care team will determine the optimal preload, afterload, contractility and heart rate for each case enrolled in THAPCA. Fluids including blood products or diuretics will be administered as needed to optimize preload. Inotropic and/or vasopressor agents will be administered as clinically indicated for contractility and blood pressure augmentation. Optimal heart rate will also be determined by the bedside clinical care team. This includes treatment of cardiac arrhythmias. The effects of hypothermia on hemodynamics in adult and neonatal trials have usually been related to heart rate with little impact on blood pressure.¹¹⁸ Bradycardia is commonly associated with decreased oxygen consumption in hypothermia treated cases.¹¹⁹ In pediatric TBI trials tachycardia was observed in some hypothermia treated patients and responded to fluid administration.³⁴

7.9 Management of Mechanical Ventilation

The requirement of mechanical ventilation support following cardiac arrest is a study inclusion criteria. It would be desirable to describe an explicit mechanical ventilator management algorithm for subjects enrolled in this study, but this is untenable because of the diversity of potential etiologies, clinical conditions, and comorbidities represented in a typical pediatric population. In general, hyperventilation should be avoided and PaCO₂ should be maintained in a normal physiologic range for age unless the primary care team determines the patient would benefit from a different range. Arterial blood gas values will not be corrected for temperature and will reported at 37 °C . It is a common practice in the PICU setting to use a lung protective strategy by limiting tidal volume and peak inspiratory or plateau pressure. The optimal FiO₂ and PEEP for the clinical case will be determined by the primary care team. The use of high frequency oscillation (HFO) after randomization is permitted. The clinical care team may administer other support therapies such as inhaled nitric oxide (NO) as clinically indicated.

7.10 Fluid and Renal Management

After cardiac arrest, patients are at high risk of renal injury that progresses to renal insufficiency or failure. In general, one would limit exposure to nephrotoxic drugs when other agents are available. Urine output less than 1 cc/kg/hr in infants and children and less than 30 cc/hr in adolescents may be inadequate. The primary caregiver team will determine the optimal preload range for a given patient and administer fluids and/or give diuretics as needed. Initiation and type of dialysis modalities if needed will also be determined by the clinical care team.

7.11 Seizure Management

The occurrence of clinical and electrographic seizures from the time of randomization through Day 7 will be recorded in the database. General guidelines for evaluation and treatment of either a clinical or an electrographic seizure are summarized as follows. A check of glucose, calcium, and electrolytes would generally be performed if not recently available. A benzodiazepine agent (i.e. lorazepam, midazolam, diazepam) would commonly be administered to stop acute seizure activity. Many patients would also receive a full loading dose of phenobarbital or phenytoin equivalent (20 mg/kg) to prevent recurrence or stop ongoing seizures. A follow-up EEG would be obtained as soon as feasible to verify that there are no on-going electrographic seizures. If there are electrographic seizures noted, these would usually be treated with additional anticonvulsant dosing, according to protocols or care management at each unit.

7.12 Special Issues of ECMO

Temperature regulation on ECMO does not require use of surface cooling (Blanketrol III unit with cooling mattresses). The desired temperature will be ordered and set by the bedside ECMO specialist by changing the temperature of the heat exchanger. Special considerations need to be made for the sedation, analgesia, and neuromuscular blockade of patients on ECMO during the intervention phase of the study. The bioavailability of midazolam and fentanyl may be reduced due to possible membrane oxygenator absorption. For patients on ECMO, lorazepam and morphine may be substituted for midazolam and fentanyl. Lorazepam will be given as a bolus of 0.1 mg/kg (100 mcg/kg) as needed to achieve a Ramsay score of 5. This will be followed by intermittent dosing of 0.1 mg/kg as needed.

Morphine will be administered as a bolus of 0.1 mg/kg (100 mcg/kg) as needed to achieve a Ramsay score of 5 or greater. Thereafter, morphine will be administered by continuous infusion beginning at 30 mcg/kg/hr. The infusion dose should be increased by 10 to 30 mcg/kg/hr only after 2 doses of morphine (0.1 mg/kg (100 mcg/kg)) are required.

Paralysis will not be required for ECMO patients unless clinical shivering is observed that is not responsive to sedation/analgesia with lorazepam and morphine.

Due to the propensity for bleeding in the ECMO patient, only one central temperature recording device is required in this population. Either a temperature sensing esophageal probe, Foley catheter or rectal probe can be used. If the clinical center has ECMO equipment that allows for the blood temperature to be measured within the circuit, then this can be substituted for a central temperature recording device (esophageal probe, Foley catheter or rectal probe).

